5.10.3 Secondary Efficacy Variables

The key secondary efficacy endpoints are change from baseline in VAS for pain score and the FACIT fatigue scale score at week 24. All efficacy analyses will be based on the ITT population in double-blind period.

5.10.3.1 Key Secondary Endpoints

- Analysis of change in VAS for pain score from baseline at week 24 using ANCOVA.
- Analysis of change in FACIT fatigue scale score from baseline at week 24 using ANCOVA.

The ANCOVA will include treatment group as fixed effect; the baseline measurements and stratification factors as covariates.

The missing data will be imputed by baseline observation carried forward (BOCF) method.

For sensitivity analysis, random hot deck multiple imputation method using a regression based approach will be conducted. In this imputation method, missing values will be replaced with values from a similar responding unit. Uncertainty with this imputation will be considered via Multiple Imputations (MI) combining rules (Rubin, 1987; Little, 1988).

- Analysis of change in VAS for pain score from baseline at week 24 using ANCOVA by hot deck multiple imputation method.
- Analysis of change in FACIT fatigue scale score from baseline at week 24 using ANCOVA by hot deck multiple imputation method.

The imputation for FACIT fatigue questionnaire written in Section 5.10.1.8 will be applied before conducting multiple imputations.

The following summary tables and analyses will also be provided:

- A summary table of change in VAS for pain score from baseline to every 24 weeks.
- A summary table of change in FACIT fatigue scale score from baseline to every 24 weeks.
- Analysis of change in VAS for pain score from baseline to every 24 weeks using MMRM analysis.
- Analysis of change in FACIT fatigue scale score from baseline to every 24 weeks using MMRM analysis.

The MMRM will include treatment group, protocol-specified visit, treatment-by-visit interaction as fixed effects; the baseline measurements and stratification factors as a covariate; and visit as a repeated measure. The unstructured covariance matrix will be assumed in the model.

If the unstructured covariance matrix does not converge, other covariance structure will be used. If treatment-by-visit interaction is not statistically significant, the full model will be kept.

If the normality assumption for the key secondary variable does not hold, GEE or Generalized Linear Mixed-effect model analysis will be used. The assessment will be performed prior to unblinding.

5.10.3.2 Other Secondary Endpoints

The following summary tables, figures and analysis will be provided for the ITT:

- A summary table of change in SF-36 domain scores from baseline to every 24 weeks.
- A summary table of change in SF-36 summary score (physical and mental) from baseline to every 24 weeks.
- A summary table of change in EQ-5D scores from baseline to every 24 weeks.
- A summary table of the proportion of relapse-free subjects.
- A summary table of ARR (protocol-defined relapse).

The ARR is calculated as the total number of relapses experienced divided by the person-years at risk. The 95% CI will be presented based on the Poisson distribution. ARR based on the person-years at risk on the total study period will also be provided. In order to account for different study treatment exposure durations among subjects, log-transformed exposure time will be included in the model as an “offset” variable for appropriate computation of ARR.

- A summary table of ARR (clinical relapse).
- A summary table of ARR (treated clinical relapse).
- Analysis of ARR will be performed using negative binomial regression model (protocol-defined relapse).

For comparing the difference between 2 treatment arms, relapse number will be the response variable; treatment group, baseline ARR and geographic region as covariates. Log-transformed exposure time will be included in the model as an “offset” variable.

- summary table of change in mRS scores from baseline to every 24 weeks.
- A summary table of change in ZBI scores from baseline to every 24 weeks.
- A summary table of change in EDSS scores from baseline to every 24 weeks.
- A summary table of change in visual acuity (Snellen chart) scores from baseline to every 24 weeks.

- Analysis of change in SF-36 domain scores from baseline to every 24 weeks using MMRM analysis.
- Analysis of change in SF-36 components (physical and mental) from baseline to every 24 weeks using MMRM analysis.
- Analysis of change in EQ-5D scores from baseline to every 24 weeks using MMRM analysis.
- Analysis of change in mRS scores from baseline to every 24 weeks using MMRM analysis.
- Analysis of change in ZBI scores from baseline to every 24 weeks using MMRM analysis.
- Analysis of change in EDSS scores from baseline to every 24 weeks using MMRM analysis.

The MMRM will include treatment group, protocol-specified visit, treatment-by-visit interaction as fixed effects; the baseline measurements and stratification factors as covariates; and visit as a repeated measure. The unstructured covariance matrix will be assumed in the model.

If the unstructured covariance matrix does not converge, compound symmetric structure will be used. If treatment-by-visit interaction is not statistically significant, the full model will be kept.

If the normality assumption for other secondary variables does not hold, GEE or Generalized Linear Mixed-effect model analysis will be used. The assessment will be performed prior to unblinding.

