#### **4.3.2.2 Satralizumab: Extension Period**

Patients who experience a relapse which is treated with rescue therapy and/or a protocol-defined relapse which is adjudicated by CEC or who complete the double-blind period can enter the *OLE* period. In the *OLE* period, the patient will receive an SC injection of satralizumab at Weeks 0, 2 and 4, and Q4W thereafter, *with the last study drug administration on or before 31 December 2021.*

The patients who are treated with rescue therapy during the double-blind period can start administration of satralizumab once disease has stabilized after the rescue therapy for the relapse, between Day 31 to Day 60, defining the day of onset of relapse in the double-blind period as Day 1. If satralizumab cannot be administered by Day 60, the Investigator should consult with the Medical Monitor. The patients who are not treated with rescue therapy during the double-blind period can enter the extension period after 4 weeks ( $\pm$  7 days) from the last dosing in the double-blind period.

Patients who experience a relapse during the extension period will continue administration of satralizumab at the discretion of the Investigator.

*In the OLE period after Week 48, and in accordance with local regulations, administration of satralizumab prefilled syringes outside of the study site (e.g., self administration or administration by a caregiver after completing training, administration by the patient's [local] general physician, or home administration by a mobile nurse) will be allowed in emergency situations such as the SARS CoV-2 (COVID-19) pandemic.*

*Following the implementation of Protocol Version 11 and in accordance with local regulations, administration of satralizumab prefilled syringes outside of the study site (e.g., self-administration or administration by a caregiver after completing training, or home administration by a mobile nurse) may be allowed on scheduled study drug administration days that do not require additional assessments that must be performed on site (Appendix 1).*

Guidelines for dosage modification and treatment interruption or discontinuation are provided in Section 5.1.

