## **6.2 DETERMINATION OF SAMPLE SIZE**

Approximately 70 patients need to be recruited and randomized in a 1:1 ratio to the two treatment groups (satralizumab and placebo). The sample size considerations are based on the following assumptions:

1. A two-sided log-rank test
2. 80% power at the 5% significance level
3. A 66.5% reduction in the risk of relapse, i.e., the TFR hazard ratio of satralizumab over placebo is 0.335
4. TFR in the placebo arm following an exponential distribution, with hazard rate  $h(t)=0.4184$
5. A 2-year dropout rate of 10%

Based on these assumptions, 26 TFR events are needed for the primary analysis. TFR events are defined as protocol-defined relapses confirmed by the CEC with EDSS/FSS assessment performed by the examining assessor within 7 days after relapse symptoms were reported to site by the patient. The maximum accrual rate is estimated to be approximately 8 patients per month, after the first patient in (FPI) plus 8 months of ramp up. The 70 patients enrolled over one year and followed for an additional one and a half years will provide 26 TFR events. The primary analysis will be performed once 26 TFR events have been observed. The Sponsor will conduct a blind review of the data including accumulation of events during the double-blind period and may take appropriate action such as to increase the number of patients or to extend the double-blind period based on this blind review.

It has been assumed that the number of relapses will follow a Gamma-Poisson distribution and that the variance/mean ratio will be a constant value of  $\sqrt{2}$ . This distribution was assumed and the ratio was estimated using data from MS trials (Gold et al. 2012; Kappos et al. 2010) because there are no approved medications for NMO and no raw data from patients with this indication are available.

Because the mean ARR of NMO patients is estimated at 0.753 (Cossburn et al. 2012) and patients entering this study have an ARR  $\geq 1$  owing to inclusion criterion 2, we calculate the zero-truncated mean of the Gamma-Poisson distribution with the mean of 0.75 and the mean and variance ratio of  $\sqrt{2}$ , then the baseline ARR is estimated at 1.6. The two Phase 3 MS trials above reported that pre- and post-baseline ARR in the placebo group were 1.4 and 0.4, so the post-baseline ARR in placebo group in this trial is estimated at 0.5.

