### **Annualized Relapse Rate**

The relapse episodes for each eligible patient will be recorded throughout the whole study. The ARR is calculated as the total number of relapses experienced divided by the person-years at risk for each year of the study period. The 95% CI will be presented based on the Poisson distribution.

For comparing the difference between *the two* treatment arms, negative binomial regression model will be used with ARR as response variable *and* treatment group, baseline ARR and geographical region as covariates.

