5.14 Determination of Sample Size

Approximately 70 subjects need to be recruited and randomized in a 1:1 ratio to the two treatment groups (SA237 and placebo). The sample size considerations are based on the following assumptions:

- A two-sided log-rank test
- 80% power at the 5% significance level
- A 66.5% reduction in the risk of relapse, i.e. the TFR hazard ratio of SA237 over placebo is 0.335
- TFR in the placebo arm following an exponential distribution, with hazard rate for one year $h(t) = 0.4184$
- A 2-year dropout rate of 10%

Based on the assumptions, 26 TFR events are needed for the primary analysis. TFR events are defined as protocol-defined relapses confirmed by the CEC with EDSS/FSS assessment performed by the examining assessor within 7 days after relapse symptoms were reported to site by the subject. The maximum accrual rate is estimated to be approximately 8 subjects per month, after the FPI plus 8 months of ramp up. The 70 subjects enrolled over one year and followed for an additional one and a half year will provide 26 TFR events. The primary analysis will be performed once 26 TFR events have been observed. Sponsor will conduct blind review during the double-blind period and might take appropriate action based on blind review.

Since the annualized relapse rate (ARR) is the number of relapse counts observed when every subject is observed for a year and suppose that the distribution follows a Gamma-Poisson distribution and that the mean and variance ratio (variance / mean) is a constant value of $\sqrt{2}$. The ratio was estimated using MS trials' data^{1,2)} because there are no approved medications for NMO.

Because the mean ARR of NMO subjects is estimated at 0.753³⁾ and eligibility criterion 2 says more than one ARR subjects are selected, we calculate the zero-truncated mean of the Gamma-Poisson distribution with the mean of 0.75 and the mean and variance ratio of $\sqrt{2}$, then the baseline ARR is estimated at 1.6. The two phase III MS trials above reported that pre- and post- baseline ARR in the placebo group were 1.4 and 0.4, so the post-baseline ARR in placebo group in this trial is estimated at 0.5.

Using the proportion of zero under supposed ARR distribution, we estimate the relapse-free rate at a year in placebo group at 65.8%. The relapse-free rate is assumed to follow the exponential distribution with a constant hazard, and then we set the hazard for one year of 0.4184 in placebo group.

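### The Poisson 95% interval for per-year and total-study ARR ignores the overdispersion the plan itself assumes, and covers about 91–92% at the plan's own variance/mean ratio

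*SAP*

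**What the plan says.** **Interval.** SAP 5.10.3.2 defines ARR as relapses over person-years and adds: "The 95% CI will be presented based on the Poisson distribution". Protocol 6.5.2 (Annualized Relapse Rate) gives the same rule.

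**Periods covered.** The protocol computes ARR as relapses "divided by the person-years at risk for each year of the study period". The SAP drops the yearly breakdown but adds: "ARR based on the person-years at risk on the total study period will also be provided". Neither document specifies an ARR for the extension alone; extension time enters through the yearly and total-study rates. SAP 5.10.3 otherwise places the secondary efficacy analyses in the double-blind period.

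**Count distribution.** Protocol 6.2 assumes that "the number of relapses will follow a Gamma-Poisson distribution and that the variance/mean ratio will be a constant value of" √2. SAP 5.14 makes the same assumption.

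**Arm comparison.** Both documents use negative binomial regression; the SAP adds log exposure time as an offset.

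**Repeat relapses.** Protocol 4.3.2.1 ends a patient's double-blind period at a relapse. In the extension a relapse does not end follow-up: "Patients who experience a relapse during the extension period will continue administration of satralizumab at the discretion of the Investigator".

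**The concern.** The interval printed beside each ARR rests on a different model from the one the plan uses to describe relapse counts and to compare the arms. If counts are overdispersed, a Poisson interval is too narrow. Protocol Version 11 lengthens the extension partly to gather long-term efficacy data, and ARR is a natural summary of those data. A reader would take the long-term rate on satralizumab as more precisely known than it is.

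**Working it through.** **Inputs.** Variance/mean c = √2 = 1.414 for a one-year count, and placebo ARR 0.5 (Protocol 6.2, SAP 5.14). Hazard ratio 0.335, with the ARR ratio taken as equal to it (Protocol 6.2), so satralizumab ARR = 0.335 × 0.5 = 0.1675. 35 patients per arm. Mean total follow-up is not stated, so 1 to 6 years is assumed. Each calculation holds one mean rate throughout; the placebo arm's switch to satralizumab in the extension is not modelled.

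**Reproducing the plan's figures.** Under Gamma-Poisson counts with mean μ and ratio c, P(0) = c^(−μ/(c−1)).
- μ = 0.5: P(0) = 1.414^(−0.5/0.414) = 0.658 and −ln P(0) = 0.4184. The plan states 65.8% and 0.4184.
- μ = 0.75: zero-truncated mean = 0.75/(1 − 0.534) = 1.61. The plan states 1.6.

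So √2 is the ratio the plan actually used.

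**One-year count.** The true standard error exceeds the Poisson one by √c = 2^(1/4) = 1.189. The normal approximation gives coverage 2Φ(1.96/1.189) − 1 = 90.1%. For the exact Poisson interval, the arm total is itself negative binomial, so coverage is a sum of negative binomial probabilities. With 35 patients it is 91.5% (ARR 0.5) and 92.3% (ARR 0.1675); with 70 patients it is 91.3% and 91.5%. Simulation agrees. With truly Poisson counts the same interval covers 95–96%.

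**Longer follow-up.** The result depends on how variance/mean grows with years t. Three readings:
- **A. Constant ratio:** variance/mean = √2 at any t.
- **B. Persistent patient rates, dispersion set separately by arm:** variance/mean = 1 + 0.414t. The dispersion is 0.414/0.5 = 0.828 on placebo and 0.414/0.1675 = 2.47 on satralizumab.
- **C. Persistent patient rates, placebo dispersion in both arms:** on satralizumab, variance/mean = 1 + 0.828 × 0.1675 × t = 1 + 0.139t. On placebo, C is the same as B.

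Exact-Poisson coverage (%), 35 patients:

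| Years | A placebo / satralizumab | B placebo / satralizumab | C satralizumab |
|---|---|---|---|
| 1 | 91.5 / 92.3 | 91.5 / 92.3 | 95.0 |
| 2 | 91.3 / 91.5 | 86.8 / 87.1 | 92.9 |
| 4 | 91.3 / 92.1 | 78.9 / 80.4 | 90.6 |
| 6 | 91.6 / 91.3 | 72.9 / 72.6 | 86.8 |

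A one-year window stays in the first row whichever calendar year it is.

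**Double-blind period.** When follow-up stops at the first event, the exact Poisson interval covers 95.5–96.7% of the underlying event rate in simulation, so nothing is lost there.

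**Replacement intervals.** In simulations under persistent rates, the intercept-only negative binomial interval and the patient-level robust Poisson interval each covered about 93–96%.

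**The case against.** The strongest objection concerns size. A reader might infer that coverage as low as 72% is a property of this plan. The documents do not support that. It needs about six mean years per patient, a relapse rate fixed for each patient over all those years, and a satralizumab dispersion three times that of placebo. None of these is stated. The plan words the variance/mean ratio as constant and takes time to first relapse as exponential, and a persistent gamma rate would not give an exponential distribution. Taken literally, the plan is reading A, and coverage stays at 91–92% throughout. This part of the objection stands.

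Reading B still cannot be dismissed. The SAP's negative binomial model with a log-exposure offset has, in its usual form, a variance/mean ratio that rises with exposure. Follow-up is also long: Protocol 3.1.3 puts the end of the double-blind period before December 2018, and dosing may run to 31 December 2021. That same model, however, usually fits one dispersion for both arms. This is reading C, under which the one-year loss on satralizumab disappears.

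Two further objections stand in part. The √2 is a planning value taken from multiple sclerosis trials, not evidence of overdispersion in this trial; but it is the plan's only stated assumption, and the Poisson interval contradicts it. And the SAP's general scope is the double-blind period, where the Poisson interval is adequate; but the sentences on yearly and total-study ARR reach beyond that scope.

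**Conclusion.** The inconsistency is real and small. For per-year and total-study ARR, where a patient can contribute more than one relapse, the Poisson interval is too narrow by about 1.19-fold and covers 91–92% at the plan's own ratio. For total-study ARR the documents support only a range:
- 91–92% at any duration if variance/mean is constant;
- about 87%, 79–80% and 73% at 2, 4 and 6 years if patient-level rates persist with arm-specific dispersion;
- about 93%, 90–91% and 87% on satralizumab if both arms share the placebo dispersion.

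A reader might also infer that the double-blind ARR interval, the negative binomial comparison or the primary log-rank test is compromised. None is: a relapse ends the double-blind period, the comparison already allows for overdispersion, and the primary test does not use ARR. The affected intervals are descriptive, on a secondary endpoint outside the gatekeeping sequence in SAP 5.10.1.4. Severity is minor.

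**What to change.** In SAP 5.10.3.2, with matching words in Protocol 6.5.2, state that for per-year and total-study ARR the 95% interval comes from a Poisson model with log person-years as offset and patient-level robust variance. A negative binomial model with the same offset is an acceptable alternative.

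Keep the exact Poisson interval in two places: the double-blind ARR, where it is adequate, and any cell with no relapses, where the log-scale model intervals cannot be computed.

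The robust version is the safer default in sparse cells. With about 35 × 0.1675 ≈ 6 relapses, the negative binomial dispersion estimate fell to zero in 40–54% of simulated samples, which in effect returns a Poisson interval.

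The cost is one sentence and somewhat wider intervals. No new data are needed.

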5.10.3.3 Examination of Adolescents

The following endpoints will be presented for the adolescent population in listings:

- TFR (protocol-defined relapse).
- EDSS scores.
- Visual acuity (Snellen chart) scores.
- SF-36 domain scores.
- SF-36 summary score (physical and mental).
- VAS for pain score.
- FACIT fatigue scale score.
- EQ-5D scores.
- mRS scores.
- ZBI scores.

5.11 Safety Evaluation

Unless otherwise specified, all safety analyses will be based upon the SAF for double blind period and All SA237 for overall period as defined in Section 5.5.

Subgroup population was defined in Section 5.5.

If we have low numbers of AEs only listings may be provided.

5.11.1 Extent of Exposure

Duration of exposure to study drug (days) is defined as date of last dose - date of first dose + 1, and will be summarized.

Number of doses and total cumulative dose of study drug will be summarized. Descriptive statistics will be presented by treatment group.

5.11.2 Adverse Events

Adverse events will be coded using most recent version of MedDRA. All summaries will be sorted alphabetically by System Organ Class (SOC) and preferred term (PT), starting with the most frequent event. All adverse events reported in whole study will be reported in listings. For AEs, if the AE intensity is missing, the worst case (severe) will be assumed. If the drug relationship is missing, the worst case (drug related) will be assumed. In summaries, multiple occurrences of the same PT event in one individual counted only once.

The following summary tables of AEs will be provided:

- An overall summary of AEs will be presented. It will include the number and percentage of subjects with at least 1 AE, serious AE, AE leading to early discontinuation of treatment, and severe AE and number of death.
- A summary of AEs by SOC and PT.
- A summary of AEs by Intensity, SOC and PT.
- A summary of AEs leading to discontinuations of treatment.
- A summary of AEs leading to drug interruption.
- A summary of adverse drug reactions (ADRs) by SOC and PT.
- A by-subject listing of all AEs.
- A by-subject listing of all AEs leading to treatment discontinuation.
- A by-subject listing of all AEs leading to drug interruption.
- A by-subject listing of all ADRs.

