##### **4.3.2.1 Satralizumab and Placebo: Double-blind Period**

The patient will receive an SC injection of satralizumab or placebo at Weeks 0, 2 and 4, and Q4W thereafter during the double-blind period. The double-blind period ends when either the patient has a relapse or the total number of protocol-defined relapses judged by the CEC reaches 26.

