5.11.5 Infections, Serious Infection, Opportunistic Infection

- Serious adverse event in “SOC: Infections and infestations” will be summarized. Opportunistic infections are defined by MedDRA basket in Appendix.. Serious infection will be provided per 100 subject-year by treatment group during the double blind period. The patient-years will be based on the double blind period for safety analysis (see section 5.2). The rate per 100 subject-years by treatment group (along with the 95% CI) will be calculated for serious infections.

The number of serious infections per 100 subject-years is calculated as:

Total number of serious infections / Total number of subject-years \times 100

The 95% CI for the number of serious infections per 100 subject-years is calculated as follows:

Exact lower 95% confidence limit = $\text{chisq}(p = 0.025, df = 2Y) / (2T)$

Exact upper 95% confidence limit = $\text{chisq}[p = 0.975, df = 2(Y + 1)] / (2T)$

where Y is the total number of serious infections, T is total number of subject-years at risk and $\text{chisq}(p, df)$ is the quantile of the upper tail probability of the X² distribution on df degrees of freedom. This approach has the advantage of providing an estimate for the upper 95% confidence limit even when the total number of serious infections is zero.

The following summary tables will be provided.

- A summary of serious infection by SOC and PT.
- Rates of serious infections by 100 patient-years.
- A by-subject listing of Infections.
- A by-subject listing of Opportunistic Infections.

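### Double-blind adverse events are summarised by patient percentages over relapse-dependent follow-up, so at the planned effect satralizumab is observed about 1.23 to 1.26 times as long and equal AE rates would show as higher percentages

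*SAP*

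**What the plan says.** **Observation window.** SAP 5.2 ends the double-blind safety period on the same day as the efficacy period: the earliest of the clinical cut-off date, the day before the first extension dose, the end of the study, or last contact. SAP 4.1 has patients who received rescue therapy start the extension 31 to 60 days after relapse onset. On dosing, Protocol 4.3.2.1 says "The double-blind period ends when either the patient has a relapse" or the 26th adjudicated relapse is reached.

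**AE measure.** SAP 5.11 analyses safety on the Safety Set for the double-blind period. Of the overall AE table, SAP 5.11.2 says "It will include the number and percentage of subjects with at least 1 AE", and each preferred term counts once per patient. The SOC and preferred-term tables (5.11.2), the SAE tables (5.11.3) and the injection-reaction summaries (5.11.7) name no denominator, so the SAP 5.2 default applies: patients in the treatment group.

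**Person-time.** SAP 5.11.5 makes one exception: "Serious infection will be provided per 100 subject-year by treatment group during the double blind period", with an exact 95% interval. SAP 5.11.1 tabulates duration of exposure from first to last dose, but no AE table uses it as a denominator. Protocol 6.6 names numbers, percentages and incidences only.

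**The concern.** Time at risk for an AE depends on relapse, which is the outcome the drug is meant to delay. The better satralizumab works, the longer its patients are followed and the more of them will have at least one AE, even if the AE rate is unchanged.

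The safety objective (Protocol 2.2) compares satralizumab with placebo. Protocol 5.7 also sends health authorities an aggregate report of clinically relevant imbalances that do not favour the test product. A reader given percentages alone cannot tell a drug effect from longer observation.

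The SAP allows for unequal exposure elsewhere: a log-exposure offset in the relapse-rate model (5.10.3.2) and person-years for serious infections (5.11.5). The general AE tables have no such allowance.

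**Working it through.** **Inputs (SAP 5.14).** The test is two-sided log-rank with "80% power at the 5% significance level". On the effect, "the TFR hazard ratio of SA237 over placebo is 0.335"; on the control arm, "we set the hazard for one year of 0.4184 in placebo group". So h = 0.4184 per year on placebo and 0.335 × 0.4184 = 0.1402 on satralizumab. Dropout of 10% over 2 years gives d = −ln(0.9)/2 = 0.0527 per year. There are 35 patients per arm, with accrual over 1 year and a further 1.5 years of follow-up. Administrative follow-up c is therefore taken as uniform from 1.5 to 2.5 years.

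**Reproducing the plan's figure.** Schoenfeld: 4 × (1.960 + 0.842)² / (ln 0.335)² = 26.25 events. Power at 26 events is 0.796. Expected events by the planned cut-off are 18.9 on placebo plus 8.1 on satralizumab, or 27.0. The plan states 26, so the inputs are read correctly.

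**Mean double-blind time.** Let L be the gap from relapse to the first extension dose. With k = h + d, and averaging over c:

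E[T] = (1 − e^(−dL))/d + e^(−dL) × (1 − e^(−k(c−L)))/k

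| Gap L | Placebo (years) | Satralizumab (years) | Ratio |
|---|---|---|---|
| 0 days | 1.29 | 1.65 | 1.28 |
| 31 days | 1.33 | 1.67 | 1.26 |
| 45 days | 1.35 | 1.68 | 1.24 |
| 60 days | 1.37 | 1.69 | 1.23 |

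At 45 days, 35 patients per arm contribute about 47.3 and 58.9 person-years. With ramped accrual and no gap the ratio is 1.26. Varying the hazard ratio at 45 days gives an exposure ratio of 1.00 at HR 1, 1.10 at 0.7, 1.18 at 0.5, 1.24 at 0.335 and 1.28 at 0.25.

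**Crude percentages under identical AE rates.** The documents give no AE rates, so a constant rate r, the same in both arms, is assumed. With a = r + d, and averaging over c:

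P(at least one AE) = r × [(1 − e^(−aL))/a + e^(−aL) × (1 − e^(−(a+h)(c−L)))/(a+h)]

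At L = 45 days:

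| r per year | Placebo | Satralizumab | Gap (points) | Gap × 35 (patients) |
|---|---|---|---|---|
| 0.1 | 12.4% | 15.3% | 2.9 | 1.0 |
| 0.3 | 31.9% | 38.6% | 6.7 | 2.3 |
| 1 | 67.1% | 76.9% | 9.7 | 3.4 |
| 4 | 93.1% | 96.7% | 3.6 | 1.3 |

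Events per 100 person-years are equal in the two arms by construction.

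**Early-clustered events.** Suppose a hazard of 3 per year confined to the first 8 weeks (0.153 years) in both arms. Each patient then expects about 3 × 0.153 = 0.46 events. Crude percentages agree, at 36.7% in each arm. The event rate is 0.46/1.35 = 34 per 100 person-years on placebo and 0.46/1.68 = 27 on satralizumab. Here the person-year rate is the misleading measure: it makes satralizumab look about 20% better.

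**The case against.** **Larger figures.** A reader might take Protocol 4.3.2.1 literally and end observation on the day of relapse. That gives 45.1 versus 57.9 person-years (ratio 1.28) and gaps of about 3.2, 7.5 and 11.6 points at 0.1, 0.3 and 1 per year. The documents do not support this for the safety tables. Protocol 4.3.2.1 concerns dosing, whereas the SAP 5.2 safety window runs to the day before the first extension dose. The gap-adjusted figures are the right ones, although patients not given rescue therapy may have a different gap.

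**Infection tables.** A reader might also infer that every other infection table is a crude percentage. SAP 5.11.5 specifies opportunistic infections, and infections generally, only as by-patient listings. Percentages for infections arise through the SOC and preferred-term tables.

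**A distorted safety conclusion.** This is too strong. No between-arm AE test is planned. The imbalance needs a relapse effect. At 35 per arm the standard errors of the three differences (0.1, 0.3 and 1 per year) are about 8, 11 and 11 points, so each expected gap is below one standard error. The direction overstates harm on satralizumab; it does not hide it. SAP 5.11.1 will show the dosing-duration difference by arm, and serious infection already has an adjusted rate.

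**Rates for everything.** Extending the 5.11.5 formula to all AEs would be wrong for injection reactions, as shown above. Its exact Poisson interval would also be too narrow for common AEs that recur within patients.

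These objections limit the size and scope of the point. They leave the main AE and SAE tables with a patient denominator over unequal, outcome-dependent follow-up.

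**Conclusion.** The point holds as a moderate descriptive bias against satralizumab in the double-blind AE and SAE summaries. At the planned hazard ratio and a 31 to 60 day gap, exposure is 1.23 to 1.26 times longer on satralizumab. Identical AE rates would then show gaps of roughly 3 to 10 points over 0.1 to 1 per year. The relative excess is largest for rare events and small for very common ones.

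This rests on exponential relapse and dropout at the planned rates, uniform accrual, constant AE hazards at assumed rates, and every relapsing patient entering the extension after the same gap. Exits after clinical relapses that are not protocol-defined were not modelled and could widen or narrow the difference. No error rate is affected. The change is worth making because it is cheap and the comparison is an explicit study objective.

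**What to change.** Beside the percentages, add exposure-adjusted rates over the SAP 5.2 double-blind safety period for:

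- any AE
- SAEs
- AEs leading to discontinuation
- the Infections and infestations SOC
- the main preferred terms

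Use the exact interval of SAP 5.11.5 for first events per person-time at risk (each patient censored at the first event) or for rare events. For common recurrent AEs, use an interval that allows for clustering within patients. Keep percentages as the measure for injection-related and injection-site reactions and other early-clustered events, and say why in a table note.

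The cost is a few table columns, with no new data. The rates assume a roughly constant hazard, which the tables should state. Protocol 1.3 reports the double-blind period as completed, so rates added to existing tables should be labelled supplementary.
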